The effect of different hemostatic agents on hemorrhage control, pain and quality of life after endodontic microsurgery

University of Turin, Department of Surgical Sciences, Dental School, Endodontics, Turin, Italy.

Running Title: Surgical glue in endodontic microsurgery

Date: 3rd February 2025

NCT number: NCT ID not yet assigned

STUDY PROTOCOL

Background

The endodontic microsurgery aims to achieve a complete cleansing and a three-dimensional obturation of the apical portion of the root canal system through a surgical approach [1]. The introduction of new technologies, instruments and materials simplified the treatment steps and elevated the success rate, allowing a greater management of the apical anatomy and a higher success rate [2]. The use of the cone beam-computed tomography (CBCT) increased the precise understanding of the root apical anatomy and of the lesion landmarks, which is critical for the clinical success [3, 4]. Moreover, the surgical microscope and the ultrasonic tips for apical preparation allowed a minimally invasive approach reducing the postoperative pain and leading to a faster wound healing [5, 6]. Nevertheless, the achievement of a correct hemostasis is fundamental during endodontic microsurgery and reduces the surgical time positively affecting the post-operative pain incidence [7-9]. Thus, the use of an appropriate hemostatic agent helps to control the bleeding inside the bone crypt and influences the post-operative prognosis [10, 11].

The ideal characteristics of the hemostatic agents are a rapid effect, easy handling, biocompatibility and lack of interference with bone and tissue healing [12]. The ferric sulfate is widely used during endodontic microsurgery due to its hemostatic properties on gingival and periapical tissues. The ferric ions released by the ferric sulfate induce blood clotting through the denaturation of plasma proteins and platelets that causes the formation of a physical barrier that stops bleeding [12]. Moreover, ferric sulfate has an astringent effect, stimulating soft tissue contraction and further hemostasis [12].

Recently, the use of medical glues for bleeding control has been proposed for general surgery [13, 14]. In particular, cyanoacrylate-based glues have been used in oral surgery as tissue adhesives to promote wound healing [15-17]. However, no data are available about the use of a surgical hemostatic glue for the management of the endodontic microsurgical field. Although these materials could perform well clinically, they may be harmful for periapical tissues and they may negatively influence the post operative outcomes [18, 19].

This study tested the clinical efficacy of a N-hexyl cyanoacrylate commonly proposed for medical applications. This material is widely used in digestive tract and visceral surgery such as laparoscopies, as well as in urogenital tract and breast surgery [13, 20]. The aim of this randomized clinical trial was to evaluate the influence of the hemostatic glue on the bleeding control, postoperative pain and quality of life compared to ferric sulfate during endodontic microsurgery.

Materials and Methods

Ethical considerations

This randomized controlled clinical trial was authorized by Local Ethics Committee and Review Board (approval code: 00272/2023, approval date: 3/2/2025, NCT number: NCT ID not yet assigned). All recruited subjects provided an informed written consent for participation in the study. The trial was written according to Preferred Reporting Items for Randomized Trials in Endodontics (PRIRATE) 2020 guidelines [21].

Eligibility criteria

Consecutive informed and consenting healthy subjects (ASA 1-2) of both genders with no medical history of systemic disease and presenting a diagnosis of symptomatic or asymptomatic apical periodontitis in correspondence of endodontically treated teeth with medium ($2-5 \text{ mm}^3$) and large ($\geq 5 \text{ mm}^3$) periapical lesions were enrolled. The diagnosis was performed clinically and radiographically through periapical radiographs and small field of view (FOV) Cone-Beam Computed Tomography (CBCT). The lesions volume and diameters were evaluated using the dedicated software Mimics 24.0 (Materialise, Belgium). Only periapical defects with one or two residual cortical walls were considered, while bone cavity designs with no cortical walls were excluded. The clinical indications for retrograde endodontic retreatment were reported for all cases: the teeth presented inadequate root canal treatment with periapical radiolucency and impossible access through orthograde retreatment due to the presence of prosthetic restorations, posts,

canal blocks and ledges. Moreover, the teeth presented an adequate coronal seal and absence of pathological periodontal records.

The subjects affected by diabetes mellitus, hypertension and hepatic or renal diseases were excluded from the study. Similarly, exclusion criteria included bleeding disorders, pregnancy and antiplatelet or anticoagulant therapy. The teeth that were considered unrestorable and the elements affected by fractures or extensive periodontal defects were also dismissed. A written consensus reporting information about the surgical procedure and the clinical and radiographical follow-up was supplied.

Sample size calculation

The sample size calculation was estimated basing on clinical outcomes. In particular, basing on the VAS score reduction as primary endpoint, a study power of 80%, with a significance level of 5%, and a standard deviation of 6.24 was calculated and 10 subjects per set group were needed.

Randomization and allocation

The patients were blind about the randomization that was performed by assigning a code. Double blinding was not possible due to the use of different hemostatic agents during the surgical procedure.

Treatment procedure

The procedure was completed by one single experienced surgeon in a sterile environment using an operating microscope (OPMI Pro Ergo, Carl Zeiss, Germany). After the administration of local anesthesia with articaine 1:100,000 (Septodont, France) and 10 minutes later lidocaine 2% with epinephrine 1:50,000 (Dentsply Sirona, USA), a full thickness mucoperiosteal flap was elevated. The debridement of the periradicular lesion was obtained using surgical curettes (Hu-Friedy) and the bone crypt was completed with

a dedicated bur (#557 SL Lindemann; Brasseler USA, Savannah, GA). After curettage, the surgeon and two independent assistants evaluated the hemorrhage degree and the visibility of the surgical field [8]. Afterwards, in group 1 (n=15) the surgical glue (IfaBond, Dipromed, Italy) was applied for the hemorrhage control in the bone crypt with a needle 23G, while in group 2 (n=19) the ferric sulfate 15.5% (Astringedent) was positioned in the surgical site through compression with a cotton pellet. The qualitative analysis of bleeding score and the visibility of the surgical site after the use of the hemostatic agent was evaluated.

The apical resection of 2-3 mm with a 0°–10° bevel angle was achieved with a surgical bur (#557 SL Lindemann; Brasseler USA, Savannah, GA). Afterwards, a solution of 2% methylene blue was used to stain the apical portion of the root to visualize anatomies, isthmuses and fractures. In both groups the preparation of the apical 3 mm was achieved following the long axis of the root with a piezoelectric device (MiniPiezon Device, EMS, Switzerland) and dedicated tips (ProUltra Surgical Tips, Dentsply Sirona, USA). Root end filling was completed with superEBA sealer (SuperSeal, OGNA, Italy). After irrigation with saline solution and the removal of the hemostatic agent, the wound site was filled with blood clot, and the bleeding recovery was measured using the hemorrhage control score and comparing data with the previous records. Afterwards, the flap was sutured with a 5-0 resorbable suture (Vicryl suture, Ethicon, Switzerland). A post-surgical protocol was presented to the patients according to Bharathi et al [8]. The patients were advised to follow a specific diet, and to dismiss hard physical exercise and smoking. Mouth rinses with chlorexidine digluconate 0.2% mouthwash for seven days were prescribed. A pharmacological prescription including optional analgesics (ibuprofen 600 mg), and no antibiotics was given in any case. All patients were booked for suture removal after five days.

Outcomes

According to a previous study, the hemorrhage control and the surgical field view were evaluated assigning a dedicated score [8]. The hemorrhage control and the surgical field view evaluation was performed two times: after the curettage of the bone lesion before the

use of the hemostatic agents, and after the hemostasis. The bleeding recovery was evaluated after the removal of the hemostatic agent.

The patients' quality of life (QoL) questionnaire Oral Health Impact Profile-14 (OHIP-14) assessed the impact of the surgical procedure on the signs and symptoms affecting the oral and general functions [8, 22]. The questionnaire evaluated different domains: functional limitations, physical pain, psychological discomfort, physical disability, psychological disability, social disability and handicap. A 5-point Likert-like scale (1 = never, 2 = hardly ever, 3 = occasionally, 4 = fairly often, 5 = very often) was introduced. Pain assessment was conducted using the Numerical Rating Scale (NRS). In this scale a 20-point difference between groups is considered clinically significant [23]. The subjects were asked to record the amount of pain they felt every day after the surgical procedure. Moreover, patients were asked to fill out the frequency of the analgesic intake from immediately after surgery up to 1 week. All subjects were requested to fill out the questionnaire and the NRS scale and to record possible symptoms during the first seven days after surgery. To ensure the correct recording of these forms, they were contacted two times in the first week to check on their status and to answer any possible dilemma regarding the filling of the documents.

Statistical analysis

A blinded statistical analysis was performed. A chi-square-test was used for the analysis of the hemorrhage control, while the Fisher t-test was utilized for the quality of life and analgesic intake. Inter-examiner reliability was assessed using Cohen's Kappa statistic. Moreover, the Mann-Whitney U test was used for pain assessment on postoperative days. The statistically significant level was settled with a P value < .05. The software SPSS Statistics v.23.0 (IBM Corp, Armonk, NY) was used for the analysis.

Keywords: endodontic microsurgery; surgical glue, ferric sulfate, cone-beam computed tomography, hemostatic agents.

Declarations

Ethics approval and consent to participate

This study was conducted according to the guidelines of the Declaration of Helsinki and approved by the Research Ethics Committee of the University of Turin – Dental School (approval code: 00272/2023, approval date: 3/2/2025, NCT number: NCT ID not yet assigned). A written informed consent to participate was obtained from all of the participants in the study.

Funding

No funding

References

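### All named between-arm tests are unadjusted although lesion volume and the pre-agent bleeding scores are available; one prespecified covariate per outcome could gain precision at little cost

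*Protocol*

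**What the plan says.** **Before treatment.** The Protocol's Eligibility criteria admit medium and large lesions, so size varies by design. They state that it was measured: "The lesions volume and diameters were evaluated using the dedicated software Mimics 24.0". Since eligibility depends on volume, a value should exist for every patient. The Outcomes section has hemorrhage control and field view scored twice, first after curettage and before the agent, then after hemostasis. Symptomatic and asymptomatic disease are both eligible, and so are two wall counts: "Only periapical defects with one or two residual cortical walls were considered". These last two appear only as conditions of entry.

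**Allocation.** Randomization and allocation describes assignment by code and mentions no stratification. Treatment procedure gives 15 patients in the glue group and 19 in the ferric sulfate group.

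**Analysis.** Statistical analysis names a chi-square test for hemorrhage control and a 'Fisher t-test' for quality of life and analgesic intake. For pain, "the Mann-Whitney U test was used for pain assessment on postoperative days". No covariate enters any of these. No between-arm test is named for field view.

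**The concern.** Neither the design nor the stated analysis uses pre-treatment information that the trial already holds. If lesion size is related to postoperative pain or quality of life, or the bleeding score before the agent to the score after it, that variation stays in the error term. With 34 patients the arms can also differ visibly on such a factor by chance. The report would then have no planned way to answer the question that follows, and an adjustment chosen after seeing the data would carry little weight.

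At stake is some power, and how readily the result can be interpreted. The false-positive rate is not at stake.

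**Working it through.** **Inputs from the Protocol.** Arms of 15 and 19; 10 per group planned; 80% power; 5% significance (two-sided assumed); "a standard deviation of 6.24 was calculated".

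**Assumed, because the Protocol does not give it.** The correlation r between covariate and outcome, taken from 0 to 0.5. Outcomes are treated as normal.

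**1. The plan's own figure.** The 10 per group cannot be reproduced, because the sample-size section states no difference. Solving backwards by the normal approximation:

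Δ = SD × √(2/n) × (1.960 + 0.842) = 6.24 × √(2/10) × 2.802 = 7.82 points, and 7.82/6.24 = 1.25 SD.

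The only difference stated anywhere is on the NRS ("In this scale a 20-point difference between groups is considered clinically significant"). Put into the same formula it gives 2 × 6.24² × 2.802²/20² = 1.5, that is 2 per group, so it was not the input if the scales match. The check below therefore uses 1.25 SD as the implied effect and 0.9 SD as an assumed smaller one.

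**2. What one covariate can gain.** Residual variance falls to 1 − r²: 0.91 at r=0.3 and 0.75 at r=0.5. That is worth 1/0.91 = 1.10 and 1/0.75 = 1.33 times as many patients, before the small cost in step 3. Simulated power, 15 vs 19:

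| Difference | r | Mann-Whitney | Rank ANCOVA, one covariate |
|---|---|---|---|
| 0.9 SD | 0 | about 69% | 69% |
| 0.9 SD | 0.3 | about 69% | 71% |
| 0.9 SD | 0.5 | about 69% | 79% |
| 1.25 SD | 0.3 | 92% | 94% |

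Repeated runs of 3,000 to 6,000 trials at 0.9 SD gave 67–69% for Mann-Whitney, and 67–69%, 71–73% and 78–79% for rank ANCOVA at the three values of r. With no true difference, rank ANCOVA rejected in about 5% of trials (4.6–5.5%).

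**3. What it can cost.** In the t-test approximation with N=34 and k covariates, chance covariate imbalance inflates the variance by (N−3)/(N−3−k), and the degrees of freedom fall to N−2−k.

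- For k=1 the inflation is 31/30. Break-even R² is 1 − 30/31 = 0.032, or 0.034 once the lost degree of freedom is counted (r just under 0.2).
- Take the difference that gives the unadjusted test 80.0% power (6.23 points, 1.00 SD). One unrelated covariate lowers power to 78.6%. One with R²=0.25 raises it to 88.9%.
- For k=3 the break-even is R² = 1 − 28/31 = 0.097, and three unrelated covariates lower power to 75.6%.

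**4. Chance imbalance.** The standard error of a standardised baseline difference is √(1/15 + 1/19) = 0.345. The probability that it exceeds 0.3 SD in either direction is 2 × (1 − Φ(0.3/0.345)) = 0.385. A 0.3 SD imbalance shifts the outcome difference by 0.3r: 0.09 SD at r=0.3 and 0.15 SD at r=0.5.

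**The case against.** The strongest reply is that nothing here is an error. Unadjusted Mann-Whitney and chi-square tests after randomisation hold their size, and their p-values already allow for chance imbalance. The Protocol calls none of these variables prognostic, and adjustment is often left to an SAP, which is not at hand. Much of this stands: the point is one of efficiency. It does not dispose of the point, because the Protocol does not defer its methods. It names a specific unadjusted test for these outcomes, and a better use of the same data is available.

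Three stronger readings are tempting, and the documents do not support them.

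- *A reader might infer that the unadjusted comparison is biased, or that an imbalance would be mistaken for an effect of the agent.* It is unbiased over randomisations, and the shift in step 4 is modest unless r is large.
- *A reader might infer that precision is certainly lost.* That requires r above about 0.2. The Protocol gives no correlation, and at the 1.25 SD effect its own sample size implies, the gain is only about 2 points at r=0.3.
- *A reader might infer that wall count and symptomatic status are recorded baseline data, and that all three factors should be adjusted for.* Recording of those two is inferred from eligibility alone, and three covariates in 34 patients would need R² of about 0.10 merely to break even.

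The simulation also assumes normal outcomes. Tied or skewed scores, and ordinal models, were not tested.

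**Conclusion.** The point holds as a modest, inexpensive improvement and not as a fault in validity. The stated tests are sound but leave unused one pre-treatment measurement relevant to each main outcome. Under the assumptions above, one covariate changes power for a 0.9 SD difference by nothing at r=0, about 2 points at r=0.3 and about 10 at r=0.5. If the covariate is useless the loss is about 1 point. The balance favours adjusting for one covariate; it does not favour adjusting for several. The size of any gain is unknown until r is known. For the bleeding and field-view scores the figures are only indicative, because those scores may have few levels.

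**What to change.** Leave randomisation unchanged. In Statistical analysis, prespecify one covariate per outcome:

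- **Pain and OHIP-14:** rank ANCOVA with log lesion volume as the covariate. If the covariate is ranked too, as in the simulation, the log makes no difference.
- **Hemorrhage control and field view:** compare the post-agent scores adjusted for the same score taken before the agent.
- **All of these:** report the planned unadjusted tests alongside.

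Symptomatic status may replace lesion volume for pain only if it is confirmed as recorded for every patient and the choice is made before unblinding. The analysis of analgesic intake can stay as it is.

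Cost: a few lines of text, no new data and one degree of freedom per analysis, about 1 power point by the t-test approximation (80.0% to 78.6%) if the covariate is unrelated to the outcome.

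### Hemorrhage control is scored by degree but tested with a chi-square that ignores order; with three or more grades, a Mann-Whitney test would have more power at 15 vs 19

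*Protocol*

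**What the plan says.** The Statistical analysis section assigns one test to this outcome: "A chi-square-test was used for the analysis of the hemorrhage control". It mentions no trend or linear-by-linear version. The same paragraph says that "the Mann-Whitney U test was used for pain assessment on postoperative days".

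The outcome itself is described in three places:
- Treatment procedure, before the agent: "the surgeon and two independent assistants evaluated the hemorrhage degree and the visibility of the surgical field".
- Treatment procedure, after the agent: "The qualitative analysis of bleeding score and the visibility of the surgical site after the use of the hemostatic agent was evaluated".
- Outcomes: "the hemorrhage control and the surgical field view were evaluated assigning a dedicated score", by reference to a cited study, and "The hemorrhage control and the surgical field view evaluation was performed two times", before and after hemostasis.

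The protocol does not give the number of grades. The Treatment procedure section gives 15 patients in the glue group and 19 in the ferric sulfate group.

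The aim, at the end of the Background, is to "evaluate the influence of the hemostatic glue on the bleeding control, postoperative pain and quality of life compared to ferric sulfate". The sample size was set "basing on the VAS score reduction as primary endpoint", so hemorrhage control is not the endpoint named as primary.

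**The concern.** A degree of hemorrhage has a direction. The Pearson chi-square test asks only whether the two arms have different distributions over the categories, so relabelling the grades in any order leaves its p value unchanged. It spreads its power over every kind of difference, including patterns a hemostatic agent would not be expected to produce. A rank test concentrates on a shift toward less or more bleeding, which is the natural clinical question.

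Bleeding control comes first in both the title and the aim. With 34 patients there is little power to spare, so discarding the order makes it more likely that a real difference between the agents is missed. The loss is one of power; the validity of the chi-square test is not in question.

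**Working it through.** **Inputs from the protocol.** Arms of 15 and 19 (Treatment procedure); significance level 0.05, taken as two-sided (Statistical analysis). The protocol gives no power figure for hemorrhage control, so there is none to reproduce.

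**Assumed inputs.** Number of grades (2, 3 or 4), their distribution, and the effect size (0.5, 0.8 or 1.0 SD on a latent normal scale cut into grades).

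**Step 1: a worked example of what order contributes.** Take hypothetical grades 8/5/2 (n = 15) and 4/6/9 (n = 19). The grade totals are 12, 11 and 11.

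*Chi-square.* Expected counts are total × arm size / 34: 5.29, 4.85, 4.85 in the arm of 15 and 6.71, 6.15, 6.15 in the arm of 19. The sum of (observed − expected)²/expected is 5.48 on 2 degrees of freedom, so p = 0.064.

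*Mann-Whitney.* The midranks of the three grades are 6.5, 18 and 29.
- Rank sum in the arm of 15: W = 8×6.5 + 5×18 + 2×29 = 200.
- Expected value: 15×35/2 = 262.5.
- Tie-corrected variance: (15×19/12) × [35 − Σ(t³ − t)/(34×33)] = 23.75 × (35 − 4356/1122) = 739.0.
- z = (200 − 262.5)/√739.0 = −2.30, so p = 0.022 (exact p = 0.021).

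Now swap the labels of the first two grades. The chi-square p value stays at 0.064. W becomes 5×6 + 8×17.5 + 2×29 = 228, z = −1.27, and the Mann-Whitney p value rises to 0.20. Only the second test uses the order.

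**Step 2: power by simulation, 15 vs 19.** Pearson chi-square without continuity correction against tie-corrected Mann-Whitney, 40,000 runs per setting:

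| Grades | Shift | Chi-square | Mann-Whitney |
|---|---|---|---|
| 2, even | 1.0 SD | 56% | 56% |
| 3, even | 1.0 SD | 55% | 67% |
| 3, even | 0.8 SD | 39% | 50% |
| 3, even | 0.5 SD | 17–18% | 23% |
| 4, even | 1.0 SD | 50–51% | 71–72% |
| 4, even | 0.8 SD | 34% | 53% |
| 4, even | 0.5 SD | 15% | 25% |

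A separate run of 60,000 per setting agreed within about one point. With three or four even grades, type I error is about 5% for both tests. With uneven grades it falls to 2–4% for chi-square and stays at about 5% for Mann-Whitney.

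**Step 3: uneven grades at 1.0 SD.** Results depend on whether the shift is away from or toward the crowded grade:

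| Control split (%) | Away: chi-square vs Mann-Whitney | Toward: chi-square vs Mann-Whitney |
|---|---|---|
| 10/30/60 | 62% vs 71% | 32% vs 51% |
| 5/15/80 | 54% vs 65% | 8% vs 22% |
| 5/15/30/50 | 56% vs 74% | 33% vs 59% |

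These use the asymptotic Mann-Whitney. The exact version, which sparse tables call for, gains less: 44% vs 33% for 10/30/60 toward the crowded grade, and 11% vs 8% for 5/15/80. With even grades it reaches 65% (three) and 70% (four).

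**Step 4: a different model.** Under proportional odds with an odds ratio of 5, power is 55.6% vs 65.6% (three even grades) and 51.3% vs 68.9% (four even grades). Over odds ratios 3 to 8, the gain is about 7 to 14 points with three grades and 13 to 18 with four.

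**Step 5: the loss expressed in patients.** To match Mann-Whitney at 34 patients, chi-square needs about 43 (1.0 SD) to 47 (0.5 SD) with three even grades, and about 50 to 57 with four.

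**The case against.** The strongest objection is that the argument depends on a number the protocol does not give. The score is defined only by a cited study. The word qualitative, paired with a chi-square test, would fit a simple controlled/not-controlled reading, for which chi-square is an ordinary choice and Mann-Whitney gains nothing. This stands as a condition on the point. It does not remove it: a score of degree suggests ordered grades, and the proposed wording keeps chi-square or Fisher's exact test for two grades.

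Second, no contradiction is shown. The chi-square test is valid, and using Mann-Whitney for pain does not oblige its use here. That is correct. The point is about efficiency, and pain is cited only to show that an order-respecting test is already in the plan.

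Third, every effect size is assumed, and 1.0 SD is large. At 0.5 SD both tests are badly underpowered. The gain also needs a shift in one direction: for 45/10/45 against even thirds, chi-square has 26% power and Mann-Whitney 6%. Both limits stand, although a pure difference in spread is not the effect of interest for a hemostatic agent.

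Fourth, the protocol does not say which assessment the chi-square covers. There are scores before the agent, after it, and at bleeding recovery. The post-agent comparison between arms is the natural reading, but it is an inference.

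**Conclusion.** The concern holds, conditionally. If the score has three or more grades and the agents differ in one direction, the stated chi-square loses power against Mann-Whitney at 15 vs 19. With even grades the loss is about 6 to 12 points for three grades and 10 to 21 for four, over shifts of 0.5 to 1.0 SD. In sparse, uneven tables the gain with the exact test can be as small as about 3 points, but the exact test stayed above chi-square in every setting run with three or more grades. With two grades there is no gain.

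The grade counts, distributions and effect sizes are all assumptions. The finding affects power for an outcome named first in the title and aim; it does not affect the named primary endpoint or the validity of the test. It is a worthwhile, inexpensive improvement, held with medium confidence because the number of grades is unknown.

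**What to change.** State the number of grades in the hemorrhage score. If there are three or more, replace the chi-square with a two-sided, tie-corrected Mann-Whitney test of the post-agent score between arms, using the exact version if grades are sparse. Keep chi-square or Fisher's exact test only for a two-grade score.

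Stratifying by the pre-agent score (van Elteren) is optional. At 1.0 SD with even grades it adds 7 to 8 points when the pre/post correlation is 0.6, but costs 1 to 3 points at 0.3 and 3 to 6 at zero.

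The cost is one sentence and slightly more analysis work, with no new data. Power against non-monotone differences falls. Relative to the asymptotic Mann-Whitney, the exact version gives up 1 to 2 points with even grades and 1 to 10 with uneven ones.

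The protocol is written in the past tense with group sizes already given. If hemorrhage results have been seen, label the change post hoc and report the chi-square result beside it.

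### The primary pain endpoint is not tied to one comparison: no day, contrast or summary is named, while daily scores are tested over a week at 5%

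*Protocol*

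**What the plan says.** - **Aim (end of Background).** The trial is meant "to evaluate the influence of the hemostatic glue on the bleeding control, postoperative pain and quality of life compared to ferric sulfate". Pain is one of three targets, and no time point is attached to it.
- **Sample size calculation.** The number of patients is justified by "basing on the VAS score reduction as primary endpoint, a study power of 80%, with a significance level of 5" per cent, with an SD of 6.24 and 10 patients per group. No day, starting score or target difference is given.
- **Outcomes.** Pain is measured on an NRS, not a VAS. "The subjects were asked to record the amount of pain they felt every day after the surgical procedure", and patients were to "fill out the questionnaire and the NRS scale and to record possible symptoms during the first seven days after surgery". No pain score before surgery is described, and no outcome is labelled primary. On the size of effect: "In this scale a 20-point difference between groups is considered clinically significant".
- **Statistical analysis.** "the Mann-Whitney U test was used for pain assessment on postoperative days". "The statistically significant level was settled with a P value < .05". No primary day and no summary over days is named.
- **Treatment procedure.** The arms are given as 15 (glue) and 19 (ferric sulfate).

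**The concern.** A 5% significance level means something only for a defined comparison. Here the primary endpoint is named once, as a reduction, and the only analysis of pain described is a test of daily scores. The two do not meet. If the reduction is a change within each patient, it needs a start and an end, and neither is identified among the scores collected. If it means lower pain in one arm than in the other, the day or summary is still missing.

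The natural reading of the analysis text is one unadjusted test per day, although the protocol does not say so outright. Nor does it say whether one significant day would be enough. The primary result could therefore be any of seven days, an average, or a change between two days, and the choice could be made with the results in view. The conclusion on the trial's primary outcome would then not carry the error rate on which the sample size rests.

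**Working it through.** **1. Does the sample size identify the comparison?**

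Inputs from the Sample size calculation: n = 10 per group, SD = 6.24, power 80%, level 5% (two-sided is my assumption). No target difference is given, so the 10 cannot be reproduced. It can only be solved backwards.

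- Normal approximation: difference = SD × (1.960 + 0.842) × √(2/10) = 6.24 × 2.802 × 0.447 = 7.82 points.
- t-test version: standardised difference 1.325, and 1.325 × 6.24 = 8.27 points.
- One-sided: 6.94 (normal) or 7.22 (t).

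None of these figures appears in the protocol. The only pain difference it states is 20 points on the NRS. Using that: n = 2 × 2.802² × 6.24² / 20² ≈ 1.5, so 2 per group. The 20 points are therefore not the basis of the 10, and the sample size does not reveal which day or contrast was meant.

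**2. How many candidate tests?**

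Daily recording over the first seven days gives seven daily comparisons. This count is read from the Outcomes section; the protocol does not state it. If the seven tests were independent, the chance of at least one P < .05 under no effect would be 1 − 0.95⁷ = 0.302. Scores from the same patient are correlated, so the real figure is lower.

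**3. Seven correlated Mann-Whitney tests, 15 against 19, no true difference**

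Continuous scores, 20,000 runs per cell; the correlations are assumptions:

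| Between-day correlation | Exchangeable | AR(1) |
|---|---|---|
| 0.3 | 26.5% | 28.3% |
| 0.5 | 22.0% | 25.5% |
| 0.7 | 17.7% | 22.2% |
| 0.9 | 11.8% | 15.0% |

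A second simulation used scores rounded and clipped to 0–100. It covered SDs of 15, 20 and 25; four mean trajectories, from flat to almost all zeros by day 4; and nine correlation structures (exchangeable 0.3–0.95, AR(1) 0.5–0.95). That makes 3 × 4 × 9 = 108 scenarios, each with 20,000 runs and a tie-corrected test:

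| Rule for claiming a pain difference | False-positive rate |
|---|---|
| Any day with P < .05 | 9.9–28.1% |
| Any day with P < .05 and a mean difference of at least 20 points that day, SD 15 | under 0.1% |
| The same, SD 20 | 0.3–2.2% |
| The same, SD 25 | 1.3–8.7% |
| One test of the seven-day mean | 4.6–5.2% |
| One test on day 1 | 4.6–5.4% |

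The any-day rate hardly depends on the SD, because the test uses ranks. It stays in the same range at an SD of 6.24.

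**The case against.** The strongest objection is that the 10–28% belongs to a rule the protocol does not contain. The daily tests could be meant descriptively. If a day also had to show 20 points, the rate would fall below 5% in every scenario at SD 15 or 20, and at an SD of 6.24 no false positives appeared in a short run. This stands: the figures do not measure inflation in this trial. They do show that the error rate runs from almost nothing to over a quarter, depending on a rule nobody has written down.

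Second, reduction may mean lower pain in one arm than in the other, which needs no baseline. That is a fair reading, so the missing baseline is an ambiguity and not a proven gap. The missing day or summary remains under either reading.

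Third, the protocol says the statistical analysis was blinded. Blinding limits picking a day that favours a preferred arm. It does not prevent picking a day with a small P value, which is visible with the arms coded.

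Fourth, a separate SAP may exist. Handling of the secondary daily comparisons could properly sit there. The time point or summary of the primary endpoint could not: the protocol fixes the primary endpoint, level, test and sample size itself, and the sample size depends on what is compared.

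Finally, the VAS/NRS mismatch, the missing target difference and the unstated NRS range are separate defects. The conclusion does not rest on them.

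**Conclusion.** The concern holds. The protocol commits to one primary pain endpoint at 5% but names no day, contrast or summary by which to test it, and the analysis it describes offers several candidates at the same level. The claim can therefore be selected after the data are seen.

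The size of the problem is conditional. If any significant day could carry the claim, the false-positive rate is about 10–28%, assuming seven tests, arms of 15 and 19, and between-day correlations of 0.3–0.95. A single prespecified test keeps it near 5% under the same assumptions. This should be corrected. Confidence is moderate, because the any-day reading is plausible but not written.

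**What to change.** In Statistical analysis, name one primary pain comparison, tested once. Possible wording: *The primary endpoint is each patient's mean NRS pain score over postoperative days 1–7, compared between arms by one two-sided Mann-Whitney test at 5%.* One named day would serve equally, as would one defined reduction with its instrument, baseline and end day. If the mean is used, add a rule for missing diary days.

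Make the daily comparisons secondary, reported as estimates with confidence intervals or Holm-adjusted. In Sample size calculation, use the same instrument and endpoint, and state the target difference and SD on that scale. Confirm that the NRS runs 0–100, since a 20-point difference is impossible on 0–10.

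**If pain data have been seen.** The text is in the past tense and the arm sizes are already fixed, so this is possible. In that case date the choice, label it post hoc, and report all seven days. The result can then no longer be presented as prespecified.

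**Cost.** The mean or a named day needs no new data. A reduction from before surgery would need a score that the protocol does not describe. With 15 and 19 patients, one test at 5% has 80% power for about 1.0 SD (t-test approximation, 0.998). Keeping all seven days, the first Holm step (0.05/7 = 0.0071) needs about 1.3 SD on a day (1.294). The drawback of the mean is that an effect confined to one day is diluted; if such an effect is expected, name that day instead.
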